The present study will be conducted in multiple independent outlets in the UK OOH food sector and examine the impact of NS menu labelling. Participants will visit an outlet and be randomized to order from the restaurant's menu with calorie information or a menu with calorie information and NS labelling. The main objective of this study is to assess differences in PME according to labelling condition. Secondary objectives are to measure the effect of NS labels on the nutritional quality of food selected (UK NPM scores), energy content of the meal (both ordered and consumed) and likelihood of selecting a healthier and a less healthy option. Whether impacts of NS labelling differ based on participant characteristics will be explored (Socioeconomic Position (SEP), food choice motives) and we will also examine later food intake to assess whether there is any evidence of between condition differences (e.g., compensating for healthier meal choice in the NS condition by consuming less healthy food later in the day).

Study Information

Hypotheses:

Participants in the NS with calorie labelling condition will score higher on PME relating to the menu compared to participants in the calorie labelling only condition.

Participants in the NS with calorie labelling condition will order a meal with greater nutritional quality compared to participants in the calorie labelling only condition.

Participants in the NS with calorie labelling condition will order fewer calories from food overall compared to participants in the calorie labelling only condition.

Participants in the NS with calorie labelling condition will be more likely to choose healthier items (categorised as A/B) from the menu, and less likely to choose less healthy items (categorised as D/E) from the menu compared to participants in the calorie labelling only condition.

Design Plan

Study type: Experiment - A researcher randomly assigns treatments to study subjects; this includes field or lab experiments. This is also known as an intervention experiment and includes randomised controlled trials.

Blinding: Participants will not know the treatment group to which they have been assigned.

Is there any additional blinding in this study? To attempt to reduce the likelihood of aim guessing, participants will be recruited to a study described as 'A study of consumer behaviour in different restaurants'.

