Study design: Businesses are being actively recruited for this study. We aim to have a minimum of two outlets available for participants to visit. This study is a randomised controlled trial using a between-subjects design. Participants will be asked to visit a restaurant to eat lunch and complete some questionnaires. Participants will select one of the available restaurants to visit and will be randomly assigned to one of two conditions: Calorie labelling only or NS with calorie labelling. Later intake (over the rest of the day, after the lunch time study session) will be self-reported by participants. If one outlet is more popular than the other outlet(s), and we are not obtaining a similar number of participants for the outlets on offer, then we will actively recruit participants to each of the outlets to ensure a similar number of participants are recruited to each outlet tested.

Randomisation: Participants will be randomised to one of the two conditions. Data collection days at each of the outlets will be randomised as either NS with calorie labelling or calorie labelling only. Data collection days will be randomly assigned to condition using the RANDBETWEEN function in excel.

Sampling Plan

Existing Data: Registration prior to creation of data

Explanation of existing data: N/A

Sample

Data collection procedures: We will use an existing participant database consisting of local volunteer participants recruited through social media advertising. Only participants who have not taken part in previous similar research conducted by the appetite group at the University of Liverpool will be contacted. If required, more participants will be recruited from the local community (e.g. adverts on social media/posters in the university). Participants who sign up to the study can bring up to 4 guests with them to also take part. Tables of 5 participants were determined as the upper limit as it was deemed a manageable size for researchers to effectively monitor individual orders. Over the course of the study, we will attempt to ensure our sample is representative of the UK population in terms of gender (50% male, 50% female), age (36% aged 18-39; 64% aged 40+(31)), and SEP - education level (50% level 3 and above (2+ A-levels or equivalent, not including apprenticeships(32)).

Inclusion criteria:

- Can visit a restaurant in Liverpool city centre
- Regularly eat food prepared out of the home (from restaurants, cafes, fast food etc., at least once a month)

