- Over the age of 18 years
- Fluent English speaker

Exclusion criteria:

- Pregnant/breastfeeding
- You have been diagnosed with a current or historic eating disorder

We will check whether participants have any food allergies prior to taking part in the study and ensure that if there are allergies this information is communicated to the food outlet by a researcher. All participants will be aware of the nature of the study (i.e. consuming food/drink in a food outlet) - this will be explicitly stated in the Information Sheet. The information sheet will also draw attention to the potential risks of taking part if a participant has a food allergy and that they should consider this before deciding whether to visit the food outlet.

Procedure:

Participants will be contacted via email and asked to complete a short online screening questionnaire. Screening will ensure participants meet the inclusion criteria.

Participants that pass the screening questionnaire will be contacted to book the date and time of their meal at one of the food outlets in Liverpool city centre. There will be 6 time slots available over lunch time (between 12 and 2.30). Participants will be able to bring up to four guests with them to take part in the study. All guests must meet the inclusion criteria.

Each **study day** will be randomised to one of the two conditions:

- Calorie labelling only condition
- NS with calorie labelling condition

Upon arrival, all participants will be asked to provide verbal consent to take part in the study. The menu randomised according to day using the RANDBETWEEN function in excel (Calorie labelling only or NS with calorie labelling) will be provided to all participants, and they will order their meals and drinks with the wait staff when they are ready.

Participants will be provided with their lunch. Before serving foods, away from the view of participants, researchers will take a picture of each plate of food. Each picture will be uploaded to a personal folder labelled with each participant ID.

When they have finished each food course, plates will be cleared by wait staff and taken to another part of the restaurant, away from view of the participants. Researchers will take photographs of the plates to document any food left over, and images will be uploaded to participant personal folders. Participants will each pay for their meal once they have finished.

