An adapted version of the University of North Carolina PME scale(38) will be used to measure health concern, product attitude, and discouragement of item consumption in response to the food menu. Participants will be given the menu they ordered from to look at. All participants will answer 3 questions using a Likert scale ranging from 1 - 5 anchored by "not at all" and "a great deal". The mean response to the three items will be calculated. PME is used as an early indicator of a health message's potential to change behaviour (e.g., reduce selection of less healthy items)(17). The scale has been used previously to identify the potential impact of food labels and is predictive of long-term behaviour (39-45).

NS label of each item selected (A,B,C,D,E).

A NS category value will be recorded for each item selected by participants.

Nutritional quality of each item and for the full meal

Nutritional quality for meal choices will be calculated using the UK NPM scoring system(46). This calculates a score (continuous variable) for a product by deducting a total score for positive nutrients from a total score for negative nutrients. A lower score represents greater nutritional quality and a higher score represents poorer nutritional quality.

We will calculate the mean NPM score weighted by energy content of items for each participant. This will ensure that the NPM score of main dishes will be weighted higher than that of starters or sides (assuming energy content of selected main is higher than any starters or sides), leading to a more representative overall NPM score for food orders. This will be done using the weighted.mean function in R(47). This function multiplies each value (i.e. NPM scores for individual items) by its corresponding weight (kcal content of individual items), sums all items and then divides this by the sum of the weights.

Energy content of all food ordered

The sum of energy (kcal) across all foods ordered for the meal will be calculated

Energy and nutrients consumed

Researchers will take pictures of plates before and after each item is given to participants. Researchers will estimate the percentage of each dish consumed, by estimating the percentage of individual meal components that have been eaten. Estimations will be guided by the information available from the nutritional analysis of items, which details the proportion of the meal that is made up by individual components. For example:

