Fish and chips: Total energy comes from 41% fish, 41% chips, 12% mushy peas, 5% tartare sauce, 1% watercress.

• If 50% of chips are left (20.5% total) and 1/3 mushy peas left (4% total), then 24.5% of the meal was not eaten and 75.5% of the meal was eaten.

Participants will also be asked whether they shared any of their meal with someone else and this will be taken into account when making percentage estimates. A random 10% of percentage estimates will be performed by a second researcher to measure reliability.

Energy and nutrient consumption will be calculated by multiplying the total energy/nutritional content of food items selected/consumed by the estimated proportion of the item consumed. Nutrients explored will be salt, sugar, fat, saturated fat, protein and fibre.

Later intake

The morning after participants take part in the study, they will be emailed with a link to complete a dietary recall survey (via intake 24, https://intake24.co.uk/). Participants will report everything they ate after the study session up until they went to bed. They will be asked to provide as much detail as possible on what they had for dinner, snacks, and drinks after the study session. We will estimate based on data from Intake 24, later consumption (kcal, salt, fat, saturated fat, sugar, protein, fibre).

Participant characteristics

To characterise the sample and present outcomes by individual participant variables, participants will be asked to report their gender, age and ethnicity. Height and weight data will also be collected to calculate body mass index (BMI), so participants can be classified into underweight, healthy weight, overweight or obesity.

Highest educational qualification: measure of socioeconomic position (SEP)

Participants will be asked to report their highest educational qualification. If they are still studying, they should report the diploma they are currently studying for. The categories provided will be:

- Less than high school
- High school completion
- College or foundation degree
- Bachelor's degree
- Master's degree
- Doctoral or professional degree

Frequency of eating OOH

Participants will be asked to report how often they eat food prepared OOH. They will be provided with an explanation of what constitutes OOH (e.g., "How often over the past year on average have you eaten food prepared out of the home? This includes food from a restaurant, café, pub or similar venue"). The response options will be:

- Not in the last year

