	Control condition Participants will receive a calorie labelled menu without NS labels. The menu will include a statement that 'Adults need on average 2000 kcal per day'.	Experimental condition Participants will receive a menu with each item labelled with calorie content and a NS value (A to E, where A is the healthiest in dark green and E is the least healthy, in red). The menu will include a statement that 'Adults need on average 2000 kcal per day'. Text at the bottom of the menu will show the full Nutri-score diagram and read: " NUTRI-SCORE NUTRI-SCORE NUTRI-SCORE NUTRI-SCORE NUTRI-SCORE NUTRI-SCORE NUTRI-SCORE NUTRI-SCORE NUTRI-SCORE NUTRI-SCORE NUTRI-SCORE NUTRI-SCORE This score is calculated according to the content of energy and key dietary nutrients (e.g. saturated fat, sugar, salt, protein, fibre). This does not differentiate between fructose (i.e. sugar found in fruit) and refined sugar or directly account for vitamin/mineral contents or level of processing"			
	 The participants will be asked to order lunch from the menu. The procedure of placing orders will be finalised with the restaurant staff. When meals are ready, researchers will take a picture of each plate of food and serve to participants. A second photo of each plate will be taken when meals are finished, and plates are cleared. 				
Post-meal assessments (Qualtrics)	After finishin iPad to comp will ask them	g their meal, participants will be provided with an olete a follow-up questionnaire (Appendix D), which it o guess the aim of the study, collect information on essage effectiveness, health food choice motives,			

	demographic characteristics, and label awareness and understanding.
Reimbursement	 Participants will pay for their meals individually before being asked to complete a payment form. Participants will receive reimbursement for their time and travel and serve as an incentive for people from different SEP strata to participate.
Later intake	• After the restaurant visit (the next morning), participants will receive a link to Intake 24, an online programme used for dietary recall. This will be used to estimate intake for the remainder of the day after the study session.
Debrief	• Participants will be sent a debrief sheet which will detail the full aims of the study. (Appendix E)

Analysis Plan

Participant characteristics:

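### No masking is specified for the researchers who rate the percentage eaten, and the 10% second rating would not reveal a bias that both raters share

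*Protocol*

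**What the plan says.** Under Measured variables, Energy and nutrients consumed, the protocol states: "Researchers will estimate the percentage of each dish consumed, by estimating the percentage of individual meal components that have been eaten". The rating works from plate photographs. Known component shares from the nutritional analysis guide it, and self-reported sharing is taken into account. The resulting proportion multiplies the energy and nutrient content of each item. The quality check is: "A random 10% of percentage estimates will be performed by a second researcher to measure reliability".

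The Design Plan gives the blinding as "Blinding: Participants will not know the treatment group to which they have been assigned". The next entry asks about any additional blinding and is answered only with the neutral study title used to recruit participants.

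On allocation, the Randomisation paragraph says: "Data collection days at each of the outlets will be randomised as either NS with calorie labelling or calorie labelling only". On who is present, the Study flow table says: "When meals are ready, researchers will take a picture of each plate of food and serve to participants". On filing, the Procedure says "Each picture will be uploaded to a personal folder labelled with each participant ID" and, for cleared plates, "Researchers will take photographs of the plates to document any food left over, and images will be uploaded to participant personal folders".

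Secondary analyses plans eight linear mixed models of energy and nutrients consumed, and Inference criteria sets p<0.01 for secondary analyses.

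**The concern.** How much of each component remains is judged by eye. If the person judging knows which menu the table had, an expectation about the labels can tilt the judgement. The protocol's hypotheses are directional in favour of Nutri-Score, so there is an expectation to act on. Because the rating is a multiplier, a tendency to score one condition's plates as less eaten goes directly into energy and nutrients consumed and would be read as a label effect. The models share this multiplier, so agreement among them could be mistaken for corroboration. Nothing in the planned data would expose the problem afterwards: the only check compares two raters with each other, and neither is said to be masked.

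**Working it through.** **1. The plan's own example.** The fish and chips shares sum to 41 + 41 + 12 + 5 + 1 = 100. Left uneaten: 0.5 × 41 + 12/3 = 20.5 + 4 = 24.5%. Eaten: 100 − 24.5 = 75.5%. This reproduces the protocol's figure.

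The shares (41, 12) come from the nutritional analysis. The fractions left (one half, one third) are judged by eye. If the chips were judged 60% left and not 50%, the uneaten part would be 0.6 × 41 + 4 = 28.6% and the eaten part 71.4%, which is 4.1 points lower. The component structure fixes the weights but leaves the judged fractions open. This is one dish, and says nothing about an average tendency.

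**2. Can a rater know the condition?** Three statements matter when set side by side:
- Allocation is by day at each outlet, so everyone seen at one outlet on one day has the same menu.
- Researchers photograph and serve the plates, so those on site can know that day's menu.
- Neither blinding entry mentions raters, and no passage separates raters from on-site staff or withholds condition from them.

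**3. Does the second rating help?** Let rater 1 record the true percentage plus a condition-related bias b plus error, and rater 2 the same with independent error. The difference between raters does not contain b. Agreement can be excellent whatever b is. Ten per cent of 450 is about 45 participants' worth of estimates.

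**4. Size in kcal.** Shift = kcal ordered × rating bias. Both inputs are assumptions. The 700 kcal order lies between the protocol's cut-offs for mains, 600 and 860 kcal, which serve as a range.

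| Order | Bias (points) | Shift (kcal) |
|---|---|---|
| 700 kcal | 3 / 5 | 21 / 35 |
| 600 kcal | 2 / 5 / 10 | 12 / 30 / 60 |
| 860 kcal | 2 / 5 / 10 | 17 / 43 / 86 |

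**5. Effect on a test of percentage eaten with no true difference.** The protocol supplies N = 400 × 1.125 = 450 and alpha 0.01. Assumed: 225 per arm, a two-sided test, an SD of 15 to 25 points, and a design effect (DE) of 1 to 2. Then SE = SD × √(2/(225/DE)), and the false-positive probability is Φ(b/SE − 2.576) + Φ(−b/SE − 2.576).

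- Example: SD 20, DE 1, b = 5. SE = 20 × √(2/225) = 1.886, b/SE = 2.65, probability 53%.
- Over the whole range: 2.5% to 12% for b = 2, and 14% to 83% for b = 5, against a nominal 1%.

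A larger design effect would lower these probabilities but would leave the bias in the estimate unchanged.

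**6. Which outcomes are touched.** The Measured variables section applies the proportion eaten to energy and six nutrients. The eighth modelled outcome, fruit, vegetable and nut content, appears only under Secondary analyses and is presumably computed in the same way. PME, NPM score, energy ordered and the A/B and D/E selection outcomes depend on the questionnaire or the order and not on the rating.

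**The case against.** The strongest reply is that the protocol is silent here and not wrong, and that an operating procedure could already provide masking. A reader might infer that the raters are known to be unmasked, that the participant ID or a date on the file gives the condition away, or that rating takes place during data collection. The documents support none of these:
- They do not say who rates or what the rater sees.
- They do not describe the ID format or say that files carry a date. Days are randomised within outlets, so a date without the outlet and the day schedule need not identify the condition.
- They do not say when rating is done.

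The rating is also structured by component, so it is not a loose overall impression. A uniform downward shift would lower protein, fibre and fruit, vegetable and nut content as well, and so would not look like healthier eating throughout. None of the four hypotheses concerns consumption, and the affected models are secondary with a stricter threshold.

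All of this stands as a limit on the claim. What remains is that the protocol has an entry for additional blinding, fills it in, and leaves raters out. Masking of outcome assessment is a design matter that belongs in the protocol, whatever an unseen SAP contains. The component structure does not remove the judgement by eye, and the second rating does not test for bias.

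**Conclusion.** The point holds in a limited form. No masking of raters is specified, on-site researchers can know the condition, and the reliability check cannot detect a shared bias. The consequence is confined to the secondary models of energy and nutrients consumed at lunch. The primary outcomes, energy ordered and the selection outcomes are untouched.

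No bias has been shown, and its size and sign are unknown. The 21 to 35 kcal figure is multiplication of assumed inputs. The false-positive range also rests on an assumed SD, design effect and equal arms. They show that a modest tendency could matter, not that one exists. This is an inexpensive improvement and not a flaw that threatens the trial's main conclusions.

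**What to change.** Specify masked rating in the protocol, or state it if it is already intended:

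- Give each before/after photo pair a random code, and remove the participant ID, date and any condition field.
- Attach the item's component shares and the participant's sharing report (Appendix D, question 5a) under the same code. The protocol requires sharing to be taken into account, so a rater holding only the photographs could not complete the estimate.
- Rate the pairs in random order across days. Where possible, give raters plates from days they did not attend, since someone who served a table may recognise the meal.
- Do the 10% second rating on the same masked set.
- Unlock the link to condition only when all ratings are complete.

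The photographs are already planned, and the protocol places the label on the menu and not on the plate, so masking is feasible. The cost is file handling, including re-linking the sharing reports, and later availability of the ratings. No extra staff are needed.

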Participants will be asked to complete a questionnaire on an iPad to collect demographic information, assess health food choice motives, PME relating to the menu labels and to guess the aim of the study. Participants will also be asked to confirm the food items they ordered, whether they had any additional components such as condiments, and to report whether they shared any items with others at the table and if so, how much was shared. Participants will be given clear examples of how to report this. Upon completion of the study session, participants will complete a payment form to receive monetary reimbursement. This reimbursement will compensate participants for travel and time.

The next morning, participants will be emailed with a link to Intake 24, an online programme for dietary recall. They will be asked to report anything that had been eaten after the lunch time meal the previous day. Following this, all participants will be fully debriefed.

The restaurants in which this study will take place will be independent restaurants in Liverpool city centre. As they are small, independent businesses, they are not required to report any nutritional information. Researchers liaised with restaurant owners, chefs and front of house staff to gather the required menu information (ingredients, cooking method) to calculate the nutritional content of meals using Nutritics(33), a platform which can be used to estimate the nutritional content of meals using validated methods. The NS values for all items on the food menus of the outlets were calculated using the NS spreadsheet available online (34). There are currently three outlets where data collection is planned to take place. These are all in Liverpool city centre and are 1) a plant-based café, 2) a café in the university campus and 3) a street-food inspired café.

Variables

Manipulated variables: Whether participants are provided with a calorie labelled menu or a menu where each item is also labelled with a NS classification from A (healthiest) to E (least healthy).

Adapted NS: The NS classification was created in France to apply to packaged food products, and the calculations are made based on energy, nutrients (saturated fat, sugar, salt, fibre, protein) and fruit, vegetable and nut content per 100g of the food product. Fruit, vegetable and nut content for each menu item was estimated by two researchers individually. Any disagreements were resolved by

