Similar to the above, any participants who select a less healthy item (D/E) as part of their meal will be coded as 1, and participants who have only selected options with a A/B/C value will be coded as 0. We will conduct a logistic regression to test whether NS labelling (Y/N) is associated with the likelihood of selecting a less healthy item.

Energy and nutrient content consumed at lunch

Similar to primary analyses, we will explore the impact of NS labelling on total energy and nutrient content of food consumed (linear outcome variables) through n=8 linear mixed models. The nutrients explored will be salt, sugar, fat, saturated fat, protein, fibre and fruit vegetable and nut content.

Transformations: N/A

Inference criteria: Results for primary analyses will be considered significant at p<0.05, and to account for multiple comparisons, secondary analyses will be considered significant at p<0.01.

Data exclusion: If participants leave the restaurant study session without ordering food their data will be excluded from analyses.

Missing data: If participants do not complete the dietary recall survey, and therefore do not provide data of later intake, then we will impute the missing data for this variable. Any missing data for other outcomes (e.g., PME) will also be imputed. We will complete multiple imputation with 5 imputed datasets(50) in R using the 'mice' package. Imputation will be reported in line with published guidance(51).

Exploratory analysis:

Other:

Sample size:

We conducted a simulation to estimate sample size required for two primary outcomes: PME and NPM scores. Our simulation was based on previous research and knowledge of the outlets confirmed for data collection.

We simulated running the study with 20 participants a day for 20 days (400 total data points). For PME, we estimated from previous research that we may have an intercept PME value of 1.85 (SD: 1.08), with an intervention effect of 1 (the intervention group will have PME values 1 unit greater than the control group on average, based on previous research(52)), and minimal difference in PME

scores between the two outlets (0.2). We also assumed ICC of approximately 0.200, and a standard deviation of the random intercept of eating group in a mixed model of 1. Across 200 simulations using a regression model clustered by day, we would have 94% power (95% CI 89.75, 96.86) to detect differences in PME between the two conditions.

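### A single energy-weighted percentage of dish eaten is applied to salt, sugar, fat, saturated fat, protein and fibre, which misstates nutrient intake when a mixed dish is left unevenly

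*Protocol*

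**What the plan says.** Under Measured variables, Energy and nutrients consumed, the protocol describes three steps.

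- **Rating.** "Researchers will estimate the percentage of each dish consumed, by estimating the percentage of individual meal components that have been eaten". The component ratings are thus reduced to one percentage per dish.
- **Weighting.** The text says the nutritional analysis guides the estimate by giving each component's proportion of the meal. The only illustration, fish and chips, uses energy: "Total energy comes from 41% fish, 41% chips, 12% mushy peas, 5% tartare sauce, 1% watercress". With half the chips and one third of the peas left, it arrives at 24.5% not eaten and 75.5% eaten.
- **Conversion.** "Energy and nutrient consumption will be calculated by multiplying the total energy/nutritional content of food items selected/consumed by the estimated proportion" of the item consumed. The outcomes are then named: "Nutrients explored will be salt, sugar, fat, saturated fat, protein and fibre".

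Reliability is addressed by a second rater: "A random 10% of percentage estimates will be performed by a second researcher to measure reliability".

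In the Analysis Plan, Secondary analyses, Energy and nutrient content consumed at lunch, these quantities enter eight linear mixed models. The list there is longer by one: "The nutrients explored will be salt, sugar, fat, saturated fat, protein, fibre and fruit vegetable and nut content".

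**The concern.** A percentage built from energy shares answers one question: how much of the dish's energy was eaten. Salt, protein or fibre is not spread over a plate's components in the same proportions as energy. If the parts left behind are rich or poor in a nutrient relative to their energy, multiplying the dish's total of that nutrient by the energy percentage gives the wrong intake.

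A direct consequence is that, within any one dish, every recorded nutrient intake is energy consumed multiplied by a constant (the dish's nutrient total divided by its energy total). The plate ratings therefore add nothing to the nutrient outcomes beyond what they already add to the energy outcome. The part that depends on which components were left is lost, although the photographs and component ratings can show it.

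The second-rater check would not reveal this. It measures whether two raters agree on percentages, whereas the error arises afterwards, in the formula.

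At stake are six of the eight secondary consumption models by the wording of the rule. The seventh, fruit, vegetable and nut content, is reached only by inference, because no other derivation is given for it.

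**Working it through.** **Inputs from the protocol's worked example.** Energy shares: fish 0.41, chips 0.41, peas 0.12, tartare sauce 0.05, watercress 0.01 (sum 1.00). Fractions left: chips 0.5, peas 1/3, all others 0.

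**Step 1: reproduce the plan's figure.**

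Proportion eaten = 1 − Σ (energy share × fraction left) = 1 − 0.5 × 0.41 − 0.12/3 = 1 − 0.205 − 0.040 = 0.755.

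This matches the stated 75.5% and is a share of energy.

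**Step 2: the correct fraction for a nutrient.** Replace each component's energy share by its share of that nutrient. Let *c* and *p* be the shares of the dish's nutrient held by the chips and the peas. Then

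f = 1 − 0.5*c* − *p*/3.

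The plan records 0.755 whatever *c* and *p* are.

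**Step 3: size of the error on this plate.** The document gives no component nutrient shares, so every (*c*, *p*) below is an assumption except the third row, which uses the energy shares themselves. Relative error is 0.755/f − 1.

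| *c* | *p* | True fraction f | Recorded minus true (points) | Relative error |
|---|---|---|---|---|
| 0 | 0 | 1.000 | −24.5 | −24.5% |
| 0.10 | 0.10 | 0.917 | −16.2 | −17.6% |
| 0.41 | 0.12 | 0.755 | 0 | 0 |
| 0.30 | 0.50 | 0.683 | +7.2 | +10.5% |
| 1 | 0 | 0.500 | +25.5 | +51.0% |

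The first and last rows are the bounds for this plate, reached when the nutrient is absent from both chips and peas, or is wholly in the chips. They are not expected errors.

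**Step 4: when the error vanishes.** The rule is exact for a nutrient if the dish is eaten fully, if all components are left in the same proportion, if there is only one component, or if the weighted nutrient shares of what was left happen to equal the weighted energy shares (here 0.5*c* + *p*/3 = 0.245). For instance, if 24.5% of every component is left, the true fraction is 1 − 0.245 = 0.755 for every nutrient.

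**The case against.** The strongest counter-case has five parts.

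- **The energy basis appears only in an example.** The general text speaks of a component's proportion of the meal. This is true, but it is the only basis shown. Any other single basis, such as weight, would also fail for unevenly left dishes, though with different numbers.
- **The sizes rest on assumed nutrient shares, and the illustrated dish may not be on any study menu.** This stands. Only the formula and the 50% to 100% range follow from the document. How often study dishes have several components and are left unevenly is unknown.
- **No bias between arms is shown.** This also stands. The same formula applies in both conditions. The contrast is distorted only if the dishes chosen or the pattern of leftovers differs by condition; otherwise the effect is on levels and noise. Labels could plausibly change what is left, since the Nutri-Score menu names saturated fat, sugar, salt, protein and fibre, but the document cannot settle it.
- **Differences from dish choice are preserved.** Correct: each dish keeps its own nutrient totals. The percentage also responds to which components were left. What it misses is any departure of a component's nutrient share from its energy share.
- **Only secondary outcomes are touched, at a stricter threshold (p<0.01), and component nutrient totals would have to be built.** Both points are fair. They limit the severity and add some cost, but they do not make the stated rule correct.

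**Conclusion.** The concern holds. The protocol fixes a derivation that is exact for energy and generally wrong for the six named nutrients whenever a multi-component dish is left unevenly. On its own example, 75.5% is recorded for every nutrient while the true fraction can be anywhere from 50% to 100%, a relative error between −24.5% and +51%. Those limits follow from the leftovers in the example. Where a given nutrient falls between them depends on component shares the document does not give.

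The reach is limited. Perceived message effectiveness, the nutrient profile score of the ordered meal, energy ordered, selection of A/B and D/E items, and energy consumed are all unaffected. The average error across the trial, and any difference by arm, cannot be computed from the document. This should be corrected because the rule is stated outright and the remedy is cheap, but it does not threaten the primary conclusions.

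**What to change.** Retain the percentage eaten of each component as data. For each nutrient, compute intake as the sum over components of (fraction of the component eaten × that component's content of the nutrient), using the ingredient-based nutritional analysis already done for the menus. Keep the energy-weighted percentage for energy only.

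For fruit, vegetable and nut content, state that the same rule applies and add it to the outcome list under Energy and nutrients consumed. It was estimated at dish level ("Fruit, vegetable and nut content for each menu item was estimated by two researchers individually"), so that estimate must be split by component.

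The cost is a component-by-nutrient lookup table, a changed formula and some analyst time. The protocol does not say that nutrient totals by component already exist, so they may have to be extracted from the ingredient data. If component ratings have not been kept, the plates must be re-scored from the stored images ("Researchers will take photographs of the plates to document any food left over, and images will be uploaded to participant personal folders"), so the change is cheapest if made early. No new participant data are needed.
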